Because very few patients in Study CFD4870g were non-carriers of the risk alleles for CFH and C2/CFB, these two SNPs could not be evaluated for an association with treatment response or for the rate of GA progression in patients receiving sham treatment.

Lampalizumab—F. Hoffmann-La Roche Ltd
33/Protocol GX29176, Version 6

Clinical Study Report: lampalizumab - F. Hoffmann-La Roche Ltd/Genentech, Inc.
Protocol GX29176 Report Number 1085641

Exploratory analysis of the C3 SNP did not find a significant association with treatment response or with the rate of GA progression in patients receiving sham treatment.

Exploratory analysis of the CFI SNPs indicated that there was greater efficacy in the subgroup of patients who were carriers of the CFI risk allele compared to patients who were non-carriers of the CFI risk allele. In CFI risk allele carriers, the mean difference in GA growth between the monthly group and the sham group at Month 18 was 1.839 mm², corresponding to a reduction rate of 44% (approximately 80% CI: 25%, 63%; p=0.0037). In CFI risk allele carriers, the mean difference in GA growth between the every-other-month group and the sham group at Month 18 was 0.734 mm², corresponding to a reduction rate of 18% (approximately 80% CI: -1%, 36%; p=0.2266). In non-carriers of the CFI risk allele, there was no apparent lampalizumab treatment response in either the monthly or every-other-month group.

The prognostic effects of the CFI risk allele were also examined. In patients in the sham group, the change in GA area at Month 18 was 4.169 mm² (80% CI: 3.582, 4.756) in CFI risk allele carriers and 2.792 mm² (80% CI: 2.293, 3.292) in non-carriers of the CFI risk allele; the difference in the GA progression between CFI risk allele carriers and non-carriers was approximately 49%.

The results from the exploratory analysis suggest that the CFI risk allele may be both prognostic for a more rapid progression of GA and predictive for the treatment response to lampalizumab.

Definition of CFI Profile Biomarker

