2.1 EFFICACY OBJECTIVES

The primary efficacy objective of this study is to evaluate the efficacy of intravitreal injections of 10-mg lampalizumab administered Q4W or Q6W in CFI profile biomarker-positive and CFI profile biomarker-negative patients compared with sham control assessed by change in the GA area from baseline as measured by FAF.

The secondary efficacy objective of this study is to evaluate the effect of lampalizumab compared with sham control, with respect to:

- Macular functional response as assessed by mesopic microperimetry
- Best corrected visual acuity (BCVA) as measured by the Early Treatment Diabetic Retinopathy Study (ETDRS) chart (at a starting distance of 4 m)
- BCVA as measured by ETDRS chart (at a starting distance of 4 m) under low luminance conditions
- Binocular reading speed as assessed by the Minnesota Low-Vision Reading Test (MNRead) or by Radner Reading Charts
- Binocular critical print size as assessed by the MNRead or by Radner Reading Charts
- Patient-reported visual function as assessed by the National Eye Institute Visual Functioning Questionnaire 25-item Version (NEI VFQ-25)
- Patient-reported independent reading as assessed by the Functional Reading Independence Index (FRI Index)

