6.4.1 Primary Efficacy Endpoint

The primary efficacy endpoint is the mean change in GA area from baseline at 1 year (Week 48) as assessed by FAF.

For each biomarker group, the mean change in GA area from baseline will be compared between each active treatment arm and the pooled sham arm by use of a linear mixed-effect model. The primary analysis will be based on all available data up to 1 year, with no imputation for missing data.

The dependent variable in the mixed-effect model is the change from baseline in GA area at post-baseline visits, up to 1 year, and the independent variables are the randomized treatment group, time, treatment-by-time interaction, baseline GA area, and the randomization stratification factors of (biomarker status, baseline BCVA ETDRS chart Snellen equivalent category, sex, and microperimetry eligibility). The mixed-effect model will assume an unstructured covariance structure. If there are convergence problems with the model, then a compound symmetry covariance structure will be fitted. A similar model with two additional independent variables, the biomarker status and the interaction of treatment and biomarker status, will be used to evaluate the predictive value of the genetic-defined biomarker. Also, for patients treated with sham, a comparison of change from baseline in GA area between biomarker-positive patients and biomarker-negative patients will be performed to evaluate the prognostic value of the CFI profile biomarker.

To manage the type I error of 0.0495 (two-sided), testing of the primary endpoint will be conducted in the following sequential order:

- Step 1: lampalizumab Q4W CFI profile biomarker-positive group versus pooled sham CFI profile biomarker-positive group

If there is no statistically significant difference found in this treatment comparison at the significance level of 0.0495, then the test for the next stage will not be considered statistically significant regardless of the p-value.

- Step 2: lampalizumab Q4W CFI profile biomarker-negative group versus pooled sham CFI profile biomarker-negative group, and lampalizumab Q6W CFI profile biomarker-positive group versus pooled sham CFI profile biomarker-positive group

[figure not shown]

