Enrollment of both biomarker-positive and biomarker-negative patients allows for evaluation of the treatment benefit in both patient groups, as well as the overall enrolled population. The hypotheses of interest and order of hypothesis tests for the primary efficacy endpoint are specified in Section 4.5.1, and take precedence over that specified in the study protocol. In addition to data from exploratory analyses of Study CFD4870g, interim data from the epidemiological Study GX29633 were considered for the order of hypothesis testing.

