2.3.2 Estimated Power Based on Information from Study GX29633

The primary efficacy endpoint is the change from baseline in GA area at 1 year (48 weeks) as assessed by FAF. As specified in Section 4.5.1, the primary efficacy objectives will be assessed by analysis of the primary efficacy endpoint in the overall patient population and in the biomarker-positive group for each dosing frequency separately.

[Table 2](#) summarizes the power and minimum detectable difference for the primary endpoint analysis when evaluated for the overall patient population and the biomarker-positive group using progression rates and variability assumptions based on data from Study GX29633, a prospective epidemiological study of the progression of GA secondary to AMD (May 2017 interim analysis). Namely, calculations assumed a progression rate (mean change from baseline in GA area at 48-weeks) of 2.08 mm² for both the biomarker-positive and biomarker-negative patient groups and a SD of 1.53 mm² for the change from baseline in GA area at 48-weeks. With these assumptions, 312 patients per lampalizumab treatment arm and 156 patients per sham arm will provide 88% power to declare a difference between each lampalizumab treatment arm and the pooled sham arm in the overall patient population for a targeted difference of 0.42 mm² (approximately 20% reduction relative to sham control) in the change from baseline in GA area at 48 weeks ([Table 2](#)). Estimated power to detect specified differences in the primary efficacy endpoint within the biomarker-positive

patient population is as shown in Table 2. Calculations were based on two-sided t-tests at the $\alpha=0.0496$ level (after adjustment for the four data reviews conducted by the iDMC prior to analysis of the primary efficacy endpoint), with the assumption of a 15% dropout rate by 48 weeks.

Table 2 Power and Minimum Detectable Difference for Analysis of Primary Endpoint Using Assumptions Based on the Epidemiological Study GX29633

Endpoint Summary and Population	Target Treatment Effect	Two-Sided $\alpha=0.0496$	
		Power	MDD
Mean change from baseline in GA area at 1 year (48 weeks) in all patients (n=312 per arm)	$\Delta=0.42 \text{ mm}^2$ (approximately 20% ^a reduction) SD= 1.53	88%	0.26 mm^2 (approximately 13% ^a reduction)

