4.5.1 Primary Efficacy Endpoint

The primary efficacy endpoint is the change from baseline in GA area at 1 year (48-weeks) as assessed by FAF. The primary efficacy endpoint will be analyzed for the overall patient population (Section 4.5.1.1), in addition to being analyzed for the

biomarker-positive and biomarker-negative groups separately (Section 4.5.1.2). The hypotheses of interest and Type I error management for analyses of the primary endpoint are specified below, and take precedence over that specified in the study protocol.

The null hypotheses for the primary efficacy endpoint are the following:

- H_{01} : There is no difference between lampalizumab Q4W and sham with regard to mean change from baseline in GA area at Week 48 measured by FAF for the overall patient population.
- H_{02} : There is no difference between lampalizumab Q4W and sham with regard to mean change from baseline in GA area at Week 48 measured by FAF for the CFI-profile biomarker-positive patient population.
- H_{03} : There is no difference between lampalizumab Q6W and sham with regard to mean change from baseline in GA area at Week 48 measured by FAF for the overall patient population.
- H_{04} : There is no difference between lampalizumab Q6W and sham with regard to mean change from baseline in GA area at Week 48 measured by FAF for the CFI profile biomarker-positive patient population.

For hypothesis testing of the primary efficacy endpoint, Type I error will be controlled using a fixed sequencing approach by testing the four hypotheses (H_{01} , H_{02} , H_{03} , and H_{04}) sequentially, beginning with H_{01} . All hypothesis tests for the primary endpoint will be based on a two-sided alpha level of 0.0496. Testing for statistical significance proceeds to a subsequent hypothesis only if the tests for all prior hypotheses are significant at the 0.0496 level. Note, the study will be considered positive if the first hypothesis (H_{01}) is rejected (i.e., if a statistically significant difference is observed when comparing the lampalizumab Q4W arm with the sham pooled arm for the primary efficacy endpoint in the overall patient population).

For the primary efficacy endpoint, a number of additional subgroup analyses (Section 4.5.1.3), sensitivity analyses (Section 4.5.1.4), and supplemental analyses (Section 4.5.1.5) will be performed. Included in the sensitivity analyses are analyses to assess the robustness of the primary analysis results to missing data assumptions.

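### The SAP leaves biomarker-negative patients without an error-controlled test of their own, although the protocol's primary objective names them

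*SAP*

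**What the plan says.** Protocol 2.1 sets the primary objective as the efficacy of lampalizumab "administered Q4W or Q6W in CFI profile biomarker-positive and CFI profile biomarker-negative patients compared with sham control". Protocol 6.4.1 gives the negative group two of the four confirmatory comparisons. One is "Step 2: lampalizumab Q4W CFI profile biomarker-negative group versus pooled sham CFI profile biomarker-negative group", which shares Step 2 with Q6W in biomarker-positive patients; the other is Q6W in biomarker-negative patients, at Step 3. Protocol 3.1.1 and 6.1 plan 124 biomarker-negative patients per treatment group (3 × 124 = 372) and 80% power for a difference of 0.66 mm².

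The SAP states in Section 1 that it supersedes the protocol's analysis plan, and that the hypotheses and their order changed because of interim data from Study GX29633. Under SAP 2.3.2, "the primary efficacy objectives will be assessed by analysis of the primary efficacy endpoint in the overall patient population and in the biomarker-positive group". SAP 4.5.1 states: "Type I error will be controlled using a fixed sequencing approach by testing the four hypotheses". The sequence is H01 (Q4W, overall), H02 (Q4W, biomarker-positive), H03 (Q6W, overall) and H04 (Q6W, biomarker-positive), and the study counts as positive if H01 is rejected. Table 2 has no biomarker-negative row. SAP 4.5.2.1 carries only the overall and biomarker-positive populations into secondary testing.

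SAP 4.5.1.2 keeps a separate model in each biomarker group with estimates, 95% CIs and p-values, and adds a CI and p-value for the difference in treatment effect between the groups. SAP 2.2 still says: "Enrollment of both biomarker-positive and biomarker-negative patients allows for evaluation of the treatment benefit in both patient groups".

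**The concern.** A group named in the primary objective, with its own planned sample and a randomization stratum, no longer has a hypothesis inside the error-controlled family. What remains confirmatory for these patients is their share, about 40%, of the overall average.

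That average can be significant because of the other 60%. The possibility comes from the protocol itself. On Phase II, Protocol 1.3.2 reports: "In non-carriers of the CFI risk allele, there was no apparent lampalizumab treatment response in either the monthly or every-other-month group". The same section notes that every CFI carrier in that study also carried a risk allele at CFH and/or C2/CFB, so the Phase II non-carriers correspond to the biomarker-negative group here.

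The reason given for the change does not settle the matter. From GX29633 the SAP takes equal progression, 2.08 mm² in both groups. The protocol had assumed 3.631 and 1.645 mm². Equal progression is prognostic information and says nothing about whether the drug works equally well in both groups. If H01 is rejected and the study is declared positive in the overall population, the trial can make no error-controlled statement about whether biomarker-negative patients benefit.

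**Working it through.** **Inputs.** Two-sided alpha 0.0496 (SAP 4.5.1: "All hypothesis tests for the primary endpoint will be based on a two-sided alpha level of 0.0496"; 0.05 − 4 × 0.0001). SD 1.53 mm², sham progression 2.08 mm² and 15% dropout (SAP 2.3.2). Per arm: 312 overall, 188 biomarker-positive (Table 2), 124 biomarker-negative (Protocol 3.1.1). Pooled sham equals one lampalizumab arm in size. Completers per arm: 312 × 0.85 = 265.2; 188 × 0.85 = 159.8; 124 × 0.85 = 105.4.

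**Method.** SE = 1.53 × √(2/m) with m completers per arm; power from the two-sample t-test (non-central t).

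**Reproducing the plan.** The SAP states that "312 patients per lampalizumab treatment arm and 156 patients per sham arm will provide 88% power" for 0.42 mm². SE = 1.53 × √(2/265.2) = 0.133, and power is 88.3% with MDD 0.26 mm². For biomarker-positive patients at 0.83 mm², power is 99.8% with MDD 0.34 mm². Both agree with Table 2.

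**H01 when biomarker-negative patients have no effect.** The overall effect is (188/312) × d₊ + (124/312) × d₋ = 0.603 × d₊ + 0.397 × d₋. With d₋ = 0:

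| Biomarker-positive effect | Overall effect | Probability that H01 is rejected |
|---|---|---|
| 0.83 mm² (40%) | 0.50 mm² | 96% |
| 0.70 mm² (34%) | 0.42 mm² | 89% |
| 0.62 mm² (30%) | 0.38 mm² | 81% |
| 0.42 mm² (20%) | 0.25 mm² | 48% |

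In the first row, simulation of independent group estimates (2,000,000 draws) shows the Q4W biomarker-negative estimate at zero or worse in 48% of the trials that reject H01.

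**Biomarker-negative comparison on its own.** SE = 1.53 × √(2/105.4) = 0.211. MDD is 0.42 mm² (20% of 2.08). Power is 51% at 0.42 mm² and 97% at 0.83 mm².

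**The same comparison placed after H04.** The simulation lets the two doses share the sham group and nests biomarker-positive patients in the overall population.

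| True effect, both doses | H01 to H04 all pass | then Q4W negative | then Q6W negative |
|---|---|---|---|
| 0.42 mm² in both groups | 52% | 28% | 19% |
| 0.83 mm² in both groups | over 99% | 97% | 95% |
| 0.83 mm² positive, 0 negative | 94% | 2.5% | 0.5% |

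The last row shows what the added tests supply: H01 is rejected 96% of the time there, and the biomarker-negative Q4W test in favour of drug about 2.5%.

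**The between-group comparison in SAP 4.5.1.2.** SE = √[2 × 1.53² × (1/159.8 + 1/105.4)] = 0.272. Power at two-sided 0.05 is about 86% for a difference in effect of 0.83 mm² (0.83/0.272 = 3.06) and 34% for 0.42 mm² (0.42/0.272 = 1.55).

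**The case against.** The SAP declares the change, gives a reason for it and states that it takes precedence. Testing all randomized patients first is a legitimate strategy, and any overall test can be won by an effect concentrated in one subgroup. The Phase II biomarker result is, in the protocol's own description (3.3.2.2), exploratory and from a small sample. All of this stands.

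The protocol's scheme was not a clean standard either. Its Step 2 ran two comparisons in separate patient groups, each at 0.0495, and allowed a claim on either one. If both nulls hold once Step 1 has passed, the chance of a false claim there is 1 − 0.9505² = 9.7%. The SAP's strict sequence removes that defect, and the protocol's sequence should not be restored.

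The appended tests are also weak against a modest effect, because they are reached only after Q6W has won in both populations. Under a uniform 0.42 mm² the Q4W test delivers 28%, well below its stand-alone 51%. If the Q6W effect is only half (0.21 mm²), it delivers about 10%. That is a reason to state the power, not to omit the tests, since they cost H01 to H04 nothing.

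A reader might infer that biomarker-negative patients have been removed from the analysis, that the trial can say nothing about them, or that the switch was concealed. The documents support none of these. The patients are about 40% of H01 and H03, their results and the between-group comparison are prespecified, and the change is announced in SAP Section 1. What is missing is error control.

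**Conclusion.** The point holds as a gap in confirmatory inference. No result under SAP 4.5.1 can give an error-controlled conclusion specific to biomarker-negative patients, although Protocol 2.1 names them. A rejected H01 does not fill the gap: with no biomarker-negative effect it still occurs about 96% of the time at a 40% biomarker-positive effect, falling to about a coin toss (48%) at 20%. It is therefore too strong to say that biomarker-positive patients can carry H01 whatever the size of their effect.

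The between-group comparison is a reasonable safeguard against a large difference in effect and a poor one against a difference of 0.42 mm².

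These figures rest on the SAP's SD of 1.53 mm² in both groups, 15% dropout and the planned 188:124 split. The SAP gives no separate biomarker-negative SD from GX29633. The zero-effect case is a scenario taken from Phase II, not a forecast.

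**What to change.** 1. In SAP 4.5.1, append after H04, in the same fixed sequence at 0.0496: Q4W versus pooled sham in biomarker-negative patients, then Q6W versus pooled sham in biomarker-negative patients. Use the models already specified in 4.5.1.2.
2. In SAP 4.5.2.1, state whether secondary testing extends to biomarker-negative patients if those tests succeed.
3. Add a biomarker-negative row to Table 2: n = 124 per arm, MDD 0.42 mm², stand-alone power about 51% at 0.42 mm² and 97% at 0.83 mm². Give the delivered power through the sequence beside it: about 28% (Q4W) and 19% (Q6W) under a uniform 0.42 mm², about 97% and 95% under a uniform 0.83 mm².
4. State that rejecting H01 supports the average effect in the 60:40 enrolled mix, and is to be read with the biomarker-negative estimate and the between-group comparison.

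Tests at the end of a fixed sequence take no alpha or power from H01 to H04, and the data and models are already planned. The cost is SAP text, one table row, one gating rule and a low stated power for the added tests. If the sponsor declines item 1, items 3 (stand-alone figures) and 4 are still worth making. All of it should be settled before the sponsor is unmasked for the Week 48 analysis.

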4.5.1.1 Overall Patient Population Analysis

For the overall patient population, the mean change in GA area from baseline at Week 48 will be compared between each lampalizumab treatment arm (Q4W or Q6W) and the pooled sham arm by use of a MMRM analysis. The primary analysis will be based on all available data up to Week 48, with no imputation for missing data. The model will use absolute change from baseline in GA area at post-baseline visits, up to and including 48-weeks, as the response variable, and will include independent variables for treatment arm, study visit, treatment arm by study visit interaction, baseline GA area, and the randomization stratification factors and baseline covariates as

described in Section 4.5. Study visit will be included as a categorical variable. An unstructured covariance matrix will be used to model the within-subject errors. If there are convergence problems with the model, then a heterogeneous compound symmetry covariance structure will be used.

Point estimates, 95% CIs, and p-values for the treatment effect (difference in mean change in GA area from baseline for lampalizumab vs. sham pooled) will be calculated for each lampalizumab treatment arm on the basis of the model for each assessed timepoint, including Week 48.

4.5.1.2 Biomarker Subgroup Analyses

For each biomarker group (CFI-profile biomarker-positive and CFI-profile biomarker-negative, defined per Section 2.2), the mean change in GA area from baseline at Week 48 will be compared between each lampalizumab treatment arm (Q4W or Q6W) and the pooled sham arm by use of a MMRM analysis. The regression model will be the same as that specified for the primary analysis in the overall patient population (Section 4.5.1.1), with the exception that the model will be fit separately for each biomarker group. In addition, given a separate model fit for each biomarker group, biomarker status will not be included as an independent variable in the model. Point estimates for the treatment effect (lampalizumab vs. sham) within each biomarker group will be presented for each lampalizumab treatment arm, along with corresponding 95% CIs and p-values.

Patient profile of GA lesion size change over time will be plotted by treatment arm and biomarker group.

To compare the treatment effect in the biomarker-positive patients vs. the biomarker-negative patients, the difference in the treatment effect between biomarker-positive and biomarker-negative patient groups (as estimated from the individual models above) will be calculated. A corresponding 95% CI for the difference in the treatment effect and the associated p-value will be provided based on the property that the treatment effect estimates from the individual models are independent and asymptotically normally distributed.

4.5.1.3 Other Subgroup Analyses

Exploratory subgroup analyses will be performed to evaluate the consistency of the primary analysis results across subgroups defined by demographic and baseline characteristics. Analyses will be performed for the primary efficacy endpoint (change from baseline in GA area at Week 48) for each of the following subgroups (as appropriate per actual subgroup sample size):

- Age (<75 years, 75 to <85 years, ≥85 years)
- Sex (male, female)

- Race (White, Black or African American, Asian, American Indian or Alaskan Native, Native Hawaiian or other Pacific Islander, multiple, unknown)
 - Note: If the vast majority of patients (e.g. > 95%) are of a single race, this analysis will not be conducted.
- Geographic region
 - US and Canada
 - Western Europe (Austria, Belgium, Denmark, France, Germany, Italy, Netherlands, Portugal, Spain, Sweden, Switzerland, UK)
 - Rest of World (Argentina, Australia, Hungary, Mexico, Peru, Poland, Russia, Slovakia, Turkey)
- Baseline BCVA (< 64 letters [worse than 20/50], ≥ 64 letters [20/50 or better])
- Baseline low luminance deficit (LLD) (< 30 letters, ≥ 30 letters), where LLD = BCVA - LLVA
 - Note: The median LLD at baseline is expected to be approximately 30 letters based on data from Study GX29633.
- Baseline GA area (≤ 4DA, > 4DA), where 1 disc area (DA) = 2.54 mm²
- Baseline GA contiguity (multifocal, non-multifocal)
- Baseline GA lesion location (subfoveal, non-subfoveal)
- Tobacco use history (ever, never)

Subgroup analyses based on CFI-profile biomarker status are specified in Section [4.5.1.2](#).

For the primary efficacy endpoint, a MMRM similar to that specified for the primary analysis (Section [4.5.1.1](#)) will be used for each subgroup analysis based on the data subset for the patient subgroup of interest. Baseline covariates included in the primary analysis but no longer relevant given the subgroup of interest will be excluded from the model. The estimated treatment effects (lampalizumab vs. sham) and corresponding 95% CIs from the models will be displayed graphically for each lampalizumab treatment arm and each level of the subgroups specified (e.g. via forest plots).

